5.2.1.2 For patients $<$ 18 years of age

See [Appendix IV](#) for dosing nomograms and titrations.

Dose Level	Axitinib Dose (mg/m ² /dose PO BID)
-1 [#]	1.8 (max 4 mg/dose BID)
1*	2.4 (max 5 mg/dose BID)
2	See dose titration in Appendix IV
3	See dose titration in Appendix IV

* Starting dose

[#] If a patient was most recently dosed at the lowest dose level and requires a subsequent dose reduction, the patient must be removed from protocol therapy.

5.2.2 It is recognized that to avoid high grade toxicities, periodic breaks from axitinib dosing may benefit patients. In general, such breaks of up to 7 days per cycle will be permitted at the discretion of the treating physician. Such breaks may be considered for non-DLT related recurrent toxicities impacting a patient's quality of life.

5.2.3 If a patient experiences a Grade 4 neutropenia or Grade 4 thrombocytopenia, axitinib will be withheld. Counts should be checked twice weekly until \leq Grade 3.

5.2.3.1 If the toxicity resolves to meet eligibility or baseline within 7 days of drug discontinuation, axitinib may be restarted either at the same dose level or at one dose level lower (see [Section 5.2.1](#)) at the discretion of the treating physician. For delays of more than 7 and up to 21 days, dose reduction is required. Doses reduced for toxicity will not be re-escalated, even if there is minimal or no toxicity at the lower dose level.

5.2.3.2 If toxicity does not resolve to meet eligibility or baseline within 21 days of drug discontinuation, the patient must be removed from protocol therapy.

5.2.4 If a patient experiences Grade 3 or 4 non-hematologic toxicity, axitinib should be held until toxicity resolves to \leq Grade 2. If the toxicity resolves to \leq Grade 2 within 7 days, axitinib may be restarted either at the same dose level or at one dose level lower (see [Section 5.2.1](#)) at the discretion of the treating physician. For delays of more than 7 and up to 21 days, dose reduction is required. For delays of more than 21 days, the patient must be removed from protocol therapy.

5.2.5 **Dose Modifications for Hypertension:**

5.2.5.1 Baseline blood pressure (BP) is defined as the blood pressure obtained at the examination used for study enrollment. This baseline BP should be obtained as follows: (1) Obtain 2 serial blood pressures from the same extremity with the patient in the same position that are separated by at least 1 hour. Avoid using the lower extremity if possible. (2) The baseline BP is the average of the systolic measurements over the average of the diastolic measurements.

5.2.5.2 The upper limit of normal (ULN) is defined as a BP equal to the 95th percentile for age, height, and gender (see [Appendix III](#)) for patients < 18 years old, and 150/90 mmHg for patients ≥ 18 years old.

- The NCI CTCAE will be utilized to determine the grade of hypertension for reporting purposes.
- Elevated BP measurements should be repeated on the same day to confirm the elevation. Patients with elevated BP should have BP measurements performed at least twice weekly until BP is \leq ULN.
- Elevation in either systolic or diastolic blood pressure should be considered when following the algorithms below.
- Hypertension should be managed with appropriate anti-hypertensive agent(s) as clinically indicated. It is strongly recommended that nephrology or cardiology be consulted in the evaluation and management of hypertension.

5.2.5.3 **Adults (≥ 18 years of age):**

Patients/families will self-monitor BP at home twice weekly and will inform their physicians in the event of systolic BP ≥ 140 mmHg or diastolic BP ≥ 90 mmHg. In such instances, antihypertensive treatment will start or the dose of antihypertensives will be increased per physician discretion. Table 1 below provides guidelines for monitoring and managing axitinib-related hypertension in adult patients. If the patient was already on maximal antihypertensive treatment, the axitinib dose will be reduced by one dose level (see [Section 5.2.1](#)).

Table 1. Recommended Hypertension Monitoring and Management for Adult Patients

CTCAE Grade	Antihypertensive Therapy	Blood Pressure Monitoring	Dose Modification
Grade 1 – Pre-hypertension Systolic 120-139 mmHg Diastolic 80-89 mmHg		Standard	No change
Grade 2 – Moderate Systolic 140-159 mmHg Diastolic 90-99 mmHg	
 1) Initiate LA DHP CCB[#] treatment and if needed, after 24-48 hr Rx, increase dose in stepwise fashion every 24-48 hrs until BP is controlled or at max dose of Rx. 2) If BP still not controlled, add another antihypertensive Rx, a BB[!], ACEI[^], or ARB[*]; increase dose of this drug as described in Step 1. 3) If BP still not controlled, add 3rd drug from the list of hypertensives in Step 2; increase dose of this drug as described in Step 1. 4) If BP still not controlled, consider either 1 dose reduction of axitinib (see Section 5.2.1) or stopping axitinib.* 	BP should be monitored as recommended by the treating physician	No change except as described in Step 4
Grade 3 – Severe Systolic \geq 160 mmHg Diastolic \geq 100 mmHg	
HOLD axitinib* until systolic \leq 159 mmHg and diastolic \leq 99 mmHg.
 
BP management is identical to that for Grade 2 above with 2 major exceptions:
 
 1) If systolic $>$ 180 mmHg or diastolic $>$ 110 mmHg and the patient is symptomatic: optimal management with intensive IV support in ICU; STOP axitinib.* 2) If systolic $>$ 180 mmHg or diastolic $>$ 110 mmHg and the patient is asymptomatic: 2 new 	
BP should be monitored as recommended by the treating physician unless the patient is symptomatic with systolic $>$ 180 mmHg or diastolic $>$ 110 mmHg, in which case monitoring should be intensive.
	
HOLD axitinib* until systolic \leq 159 mmHg and diastolic \leq 99 mmHg.
 
In most circumstances, if BP cannot be controlled after an optimal trial of antihypertensive medications, consider either 1 dose reduction of axitinib (see Section 5.2.1) or stopping axitinib.*
 
If the patient requires hospitalization for

	antihypertensives must be given together in Step 1 (and dose escalated appropriately as in Step 1).		management of symptomatic systolic > 180 mmHg or diastolic > 110 mmHg, permanently discontinue axitinib, or if BP is controlled, restart axitinib at 1 dose level lower.*
--	---	--	--

LA DHP CCB [#]: long-acting dihydropyridine calcium channel blocker

BB[!]: beta-blocker

ACEI[^]: angiotensin converting enzyme inhibitor

ARB^{*}: angiotensin II receptor blockers

[figure not shown]
***NOTE:** Stopping or reducing the dose of axitinib is expected to cause a decrease in BP. The treating physician should monitor the patient for hypotension and adjust the number and dose of antihypertensive medication(s) accordingly.

5.2.5.4 Pediatrics (< 18 years of age):

Monitoring for children on axitinib will occur weekly during Cycle 1 (the period during which development of hypertension is most evident), and every other week thereafter. For patients who are dose escalated, weekly monitoring for the first cycle at the higher dose will also be required. Blood pressure will be measured with an appropriate sized cuff at rest. This can be monitored in the clinic or by alternative monitoring (home, pediatrician, alternative).

The algorithm in Figure 1 below provides guidelines for managing axitinib-related hypertension in pediatric patients.

Figure 1. Hypertension Management Algorithm for Pediatric Patients

Elevations in BP are based on systolic or diastolic pressures.

* Elevated blood pressure (BP) measurements should be repeated on the same day to confirm the elevation. Patients with elevated BP at any time should have BP measurements performed at least twice weekly until BP is within the ULN.

§ ULN (Upper Limit of Normal) is a BP equal to the 95th percentile from age, height, and gender-appropriate normal values (Appendix III).

* If BP > 25 mmHg above ULN for age (verified) or Grade 4 hypertension (HTN) at any time, hold axitinib. Axitinib should also be held for BP ≤ 25 mmHg above the ULN for > 14 days or 35 mmHg above baseline for > 14 days. Antihypertensive agents can be used to control hypertension as clinically indicated after axitinib is held.

NOTE: When axitinib is held and the patient is on antihypertensive treatment, the patient should be closely monitored for hypotension.

[^] Antihypertensive therapy should be prescribed as clinically indicated, including the use of multiple anti-hypertensive agents.

[°] Baseline BP is defined in Section 5.2.5.1.

Arm A of algorithm:

- If blood pressure (BP) \leq 95% for age, height, and gender, continue axitinib at the same dose.

Arm B of algorithm:

- If BP \leq 10 mm Hg above the ULN for age, height, and gender, continue axitinib at the same dose and recheck the BP within 72 hours.
 - If the BP is \leq ULN on recheck, continue axitinib at the same dose.
- If the BP remains above the ULN on recheck, then start antihypertensive therapy (see [Figure 1](#)) and follow Arm C of the algorithm from the point that anti-hypertensive therapy is started.

Arm C of algorithm:

- If BP is 11 to 25 mm Hg above the 95% for age, height, and gender or > 35 mmHg above baseline, start anti-hypertensive therapy (see [Figure 1](#)), continue axitinib at the same dose, and monitor BP at least twice weekly.
 - If the BP returns to \leq ULN within 14 days, continue axitinib at the same dose and continue anti-hypertensive therapy.
 - If the BP remains elevated \leq 25 mm Hg above the 95% or > 35 mm Hg above baseline for more than 14 days after the initiation of antihypertensive therapy, **hold** axitinib, monitor BP at least every 3 days, and follow Arm D of the algorithm from the point that axitinib is held. **NOTE:** When axitinib is held and the patient is on antihypertensive treatment, the patient should be closely monitored for hypotension. The antihypertensive therapy should be continued until the BP is less than the ULN.
 - If the BP increases to > 25 mm Hg above the ULN despite anti-hypertensive therapy, **hold** axitinib, but continue the anti-hypertensive agent(s). **NOTE:** When axitinib is held and the patient is on antihypertensive treatment, the patient should be closely monitored for hypotension. Monitor the BP as clinically indicated and follow Arm D of the algorithm from the point that axitinib is held.

Arm D of algorithm:

- If BP is > 25 mm Hg above the 95% for age, height, and gender **hold** axitinib, monitor BP and administer anti-hypertensive therapy as clinically indicated. **Note:** When axitinib is held and the patient is on antihypertensive treatment, the patient should be closely monitored for hypotension.
 - If the BP returns to \leq ULN within 21 days, axitinib may be restarted as described in [Section 5.2.4](#).
 - If the BP is $>$ ULN for > 21 days, the patient must be removed from protocol therapy.

Arm E of algorithm:

- If the participant develops Grade 4 hypertension, **discontinue** axitinib, monitor BP and administer anti-hypertensive therapy as clinically indicated. The patient must be removed from protocol therapy. **NOTE:** When axitinib is held and the patient is on antihypertensive treatment, the patient should be closely monitored for hypotension.

5.2.6 Dose Modifications and Adverse Event Management for Pleural Effusion and Ascites:

Pleural effusion or ascites	Non-life-threatening (Grade < 4) pleural effusion or ascites	
Treat with appropriate supportive care, which may include: non-investigational diuretics, thoracentesis, chest tube drainage, paracentesis or pleurodesis.For Grade 1 pleural effusion or Grade 1 or 2 ascites, monitor with physical exam and consider additional imaging.For Grade ≥ 2 pleural effusion or grade 3 ascites, initiate methylprednisolone (2 mg/kg/day IV) or oral equivalent with attempt to taper over 7-10 days after a minimum of 24 hours of treatment.If chest tube drainage, pleurodesis or paracentesis is required, protocol therapy should be held until at least 2 days after the procedure or chest tube removal and the patient's condition is stable.If pleural effusion or ascites resolves or is managed to achieve Grade ≤ 1 and steroids are discontinued, protocol therapy may proceed without dose reduction. If pleural effusion or ascites is not resolved/managed to Grade ≤ 1 and steroids are not discontinued within 28 days of next scheduled dose of nivolumab, discontinue protocol therapy
	Grade 4 or life-threatening pleural effusion or ascites	
Institute emergency measures per institutional guidelinesInitiate methylprednisolone 2 mg/kg/day IV or oral equivalent with plan to taper as tolerated.Permanently discontinue protocol therapy

5.2.7 Dose Modifications for Proteinuria:

5.2.7.1 **Adults**

Axitinib treatment will be held in patients with greater than 2 g proteinuria per 24 hours. If measurements of total protein and creatinine clearance become less than 2 grams proteinuria per 24 hours within 21 days, axitinib may be restarted as described in [Section 5.2.4](#). For delays of more than 21 days, the patient must be removed from protocol therapy.

5.2.7.2 **Pediatrics (< 18 years of age)**

If the urine protein/creatinine (P/C) ratio is ≤ 1.9 , continue axitinib at the same dose. If patient has Grade 3 proteinuria (P/C ratio > 1.9), a second measurement should be obtained within 72 hours. If the second measurement confirms Grade 3 proteinuria (P/C ratio > 1.9), hold axitinib and re-assess weekly. If the P/C ratio decreases to ≤ 1.9 within 21 days, axitinib may be restarted as described in [Section 5.2.4](#). Monitor the UPC weekly for 2 consecutive weeks once protocol therapy resumes. For delays of more than 21 days, the patient must be removed from protocol therapy.

5.2.8 Dose Modifications for Cardiac Toxicity:

Patients who experience \geq Grade 3 left ventricular systolic dysfunction must be removed from protocol therapy and referral to a cardiologist is recommended.

5.2.9 Dose Modifications for Diarrhea:

If Grade 3 (> 3 day duration) or Grade 4 therapy-associated diarrhea is experienced by a patient despite maximal use of anti-diarrheal medications the dose of axitinib should be reduced by one dose level for subsequent cycles (see [Section 5.2.1](#)).

5.3 **Dose Modifications for Nivolumab**

Adverse events (both non-serious and serious) associated with nivolumab exposure may represent an immunologic etiology. These adverse events may occur shortly after the first dose or several months after the last dose of treatment. Nivolumab must be withheld for drug-related toxicities and severe or life-threatening AEs as per Table 2 below. Please also refer to [Appendix V](#) for suggested management guidelines. Please note some of the guidelines include references to medications which may not be appropriate for patients < 18 years of age.

Table 2. Dose Modification Guidelines for Nivolumab-Related Adverse Events

Toxicity	Hold Treatment for Grade	Timing for Restarting Treatment	Treatment Discontinuation
Diarrhea/Colitis (age \geq 18 years)	2-3	Toxicity resolves to Grade 0-1	Toxicity does not resolve within 6 weeks of last dose or inability to reduce corticosteroid to 0.15 mg/kg (up to 10 mg) or less of prednisone or equivalent per day within 6 weeks
	4	Permanently discontinue	Permanently discontinue
Diarrhea (age < 18 years)	2-3 if not reversible within 7 days and related to drug	Toxicity resolves to Grade 0-1 (evaluate for colitis)	Toxicity does not resolve within 6 weeks of last dose or inability to reduce corticosteroid to 0.15 mg/kg (up to 10 mg) or less of prednisone or equivalent per day within 6 weeks
	4	Permanently discontinue	Permanently discontinue
AST, ALT, or Increased Bilirubin (age \geq 18 years)	2	Toxicity resolves to Grade 0-1	Toxicity does not resolve within 6 weeks of last dose
	3-4	Permanently discontinue (see exception below) ^a	Permanently discontinue
AST, ALT (age < 18 years)	2-3 if not reversible within 7 days and related to drug	Toxicity resolves to Grade 0-1 (monitor AST/ALT at least twice per week until resolution)	Toxicity does not resolve within 6 weeks of last dose
	4	Permanently discontinue (see exception below) ^a	Permanently discontinue
Type 1 diabetes mellitus (if new onset) or Hyperglycemia ^b	T1DM or 3-4	Hold nivolumab for new onset Type 1 diabetes mellitus or Grade 3-4 hyperglycemia associated with evidence of beta cell failure For Grade 2 or higher pancreatitis-associated diabetes, a patient will come off protocol therapy.	Resume nivolumab when patients are clinically and metabolically stable For Grade 2 or higher pancreatitis-associated diabetes, a patient will come off protocol therapy.
Hypophysitis	2-4	Toxicity resolves to Grade 0-1. Therapy with nivolumab can be continued while endocrine replacement therapy is instituted.	Toxicity does not resolve within 6 weeks of last dose or inability to reduce corticosteroid to 0.15 mg/kg (up to 10 mg) or less of prednisone or equivalent per day within 6 weeks.
Hyperthyroidism	3	Toxicity resolves to Grade 0-1	Toxicity does not resolve within 6 weeks of last dose or inability to reduce corticosteroid to 0.15 mg/kg (up to 10 mg) or less of prednisone or equivalent per day within 6 weeks.
	4	Permanently discontinue	Permanently discontinue

Toxicity	Hold Treatment for Grade	Timing for Restarting Treatment	Treatment Discontinuation
Hypothyroidism		Therapy with nivolumab can be continued while thyroid replacement therapy is instituted.	Therapy with nivolumab can be continued while thyroid replacement therapy is instituted.
Infusion Reaction	2 ^c	Toxicity resolves to Grade 0-1	Permanently discontinue if toxicity develops despite adequate premedication
	3-4	Permanently discontinue	Permanently discontinue
Cardiac Toxicities (Including CHF, LV systolic dysfunction, Myocarditis, CPK, and troponin)	1	
Hold dose pending evaluation and observation. (*Patients with evidence of myositis without myocarditis may be treated according as "other event")
 
Note: The optimal treatment regimen for immune mediated myocarditis has not been established. Since this toxicity has caused patient deaths, an aggressive approach is recommended. Evaluate for signs and symptoms of CHF, ischemia, arrhythmia or myositis. Obtain history, EKG, CK (for concomitant myositis), CK-MB. Repeat troponin, CK, and EKG within 2-3 days. If troponin and labs normalize may resume therapy. If labs worsen or symptoms develop then treat as below. Hold drug pending evaluation.
	Toxicity does not resolve within 6 weeks of last dose
	2, 3, 4 (Suspected myocarditis)	
Hold dose. Admit to hospital. Cardiology consult. Rule out myocardial infarction and other causes of cardiac disease. Cardiac Monitoring. Cardiac Echo. Consider cardiac MRI and cardiac biopsy. Initiate high dose methylprednisolone. If no improvement within 24 hours, add either infliximab, ATG or tacrolimus.
 
Resume therapy if there is a return to baseline and myocarditis is excluded or considered unlikely.
	Toxicity does not resolve within 6 weeks of last dose
	2, 3, 4 (myocarditis confirmed)		
Permanently Discontinue.
 
Admit to Critical Care Unit (consider transfer to nearest Cardiac Transplant Unit). Treat as above. Consider high dose methylprednisolone. Add ATG or tacrolimus if no improvement.

Neurology (Guillain-Barre Syndrome, Myesthesia, Rhabdomyolysis, Encephalitis, or Grade 3 peripheral neuropathy)	Any Grade	Permanently discontinue	Permanently discontinue
Neurology (Other)	3-4	Toxicity resolves to Grade 0-2	Toxicity does not resolve within 6 weeks of last dose or inability to reduce corticosteroid to 0.15 mg/kg (up to 10 mg) or less of prednisone or equivalent per day within 6 weeks.
Pneumonitis ^d	2	Toxicity resolves to Grade 0-1	Toxicity does not resolve within 6 weeks of last dose or inability to reduce corticosteroid to 0.15 mg/kg (up to 10 mg) or less of prednisone or equivalent per day within 6 weeks.
	3-4	Permanently discontinue	Permanently discontinue

Toxicity	Hold Treatment for Grade	Timing for Restarting Treatment	Treatment Discontinuation
Renal Failure or Nephritis	2 (if not reversible to \leq Grade 0-1 within 7 days)	Toxicity resolves to Grade 0-1	Toxicity does not resolve within 6 weeks of last dose or inability to reduce corticosteroid to 0.15 mg/kg (up to 10 mg) or less of prednisone or equivalent per day within 6 weeks.
	3 (if not reversible to \leq Grade 0-1 within 7 days), Grade 4	Permanently discontinue	Permanently discontinue
Skin – Rash	2	Toxicity resolves to Grade 0-1	Toxicity does not resolve within 6 weeks of last dose or inability to reduce corticosteroid to 0.15 mg/kg (up to 10 mg) or less of prednisone or equivalent per day within 6 weeks.
All Other Drug-Related Toxicity ^e (See Exception below) ^f	3 or Severe	Toxicity resolves to Grade 0-1	Toxicity does not resolve within 6 weeks of last dose or inability to reduce corticosteroid to 0.15 mg/kg (up to 10 mg) or less of prednisone or equivalent per day within 6 weeks.
	4	Permanently discontinue	Permanently discontinue

NOTE: Permanently discontinue for any severe or Grade 3 (Grade 2 for pneumonitis) drug-related AE that recurs or any life-threatening event.

^a For patients with liver metastasis who begin treatment with Grade 2 AST or ALT, if AST or ALT increases by greater than or equal to 50% relative to baseline and lasts for at least 1 week, then patients must come off protocol therapy.

^b The protocol distinguishes hyperglycemia responsive to insulin support from pancreatitis-associated diabetes. For the former, as long as laboratory abnormalities are addressed with appropriate supportive care, treatment may continue. For Grade 2 or higher pancreatitis-associated diabetes, patients must come off protocol therapy.

^c If symptoms resolve within one hour of stopping drug infusion, the infusion may be restarted at 50% of the original infusion rate (e.g., from 100 mL/hr to 50 mL/hr). Otherwise dosing will be held until symptoms resolve and the subject should be pre-medicated for the next scheduled dose.

^d Patients will come off study drug if steroids are required to treat drug-related pulmonary toxicity, but not if transient steroids are used to treat other pathology, such as an asthma exacerbation, for example.

^e Patients with intolerable or persistent Grade 2 drug-related AE may hold study medication at physician discretion. Permanently discontinue study drug for persistent Grade 2 adverse reactions for which treatment with study drug has been held, that do not recover to Grade 0-1 within 6 weeks of the last dose.

^f Exception: Any Grade 3 or 4 drug-related laboratory abnormality or electrolyte abnormality, that can be managed with electrolyte replacement, hormone replacement, insulin, or that does not require treatment, does not require discontinuation of nivolumab.

5.3.1 Any Grade 2 drug-related uveitis, eye pain, or blurred vision that does not respond to topical therapy and does not improve to Grade 1 severity within the re-treatment period OR requires systemic treatment must go off protocol treatment.

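### For Grade 4 hypertension in patients under 18, Section 5.2.5.4 says in one place to hold axitinib and in another to discontinue it and remove the patient from protocol therapy

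*Combined protocol and SAP*

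**What the plan says.** Section 5.2.5.4 covers axitinib-related hypertension in patients under 18. It consists of Figure 1 with its notes, then a written algorithm with Arms A to E. These are branches of the algorithm, not treatment arms.

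- **Figure 1 note.** The first sentence joins two triggers, a verified blood pressure more than 25 mmHg above the age-specific upper limit of normal (ULN) and Grade 4 hypertension: "or Grade 4 hypertension (HTN) at any time, hold axitinib". It does not mention discontinuation or removal.
- **Algorithm Arm D** (more than 25 mmHg above the 95th percentile, which is the ULN). Axitinib is held. If blood pressure returns to "ULN within 21 days, axitinib may be restarted as described in" Section 5.2.4. If it stays above the ULN for more than 21 days, "the patient must be removed from protocol therapy".
- **Algorithm Arm E** (Grade 4). "If the participant develops Grade 4 hypertension, discontinue axitinib, monitor BP and administer anti-hypertensive therapy as clinically indicated". The next sentence requires removal from protocol therapy. The closing note then gives advice for the time when axitinib is held.
- **Section 5.2.4** (general, all ages). "If a patient experiences Grade 3 or 4 non-hematologic toxicity, axitinib should be held until toxicity resolves to" Grade 2 or lower. If that happens within 7 days, restart at the same or the next lower dose level is allowed; a delay of more than 7 and up to 21 days requires a dose reduction. "For delays of more than 21 days, the patient must be removed from protocol therapy".

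**The concern.** A hold and a removal are different dispositions. In this protocol a hold has a route back to axitinib, and removal does not. A site that works from the figure and its note could treat Grade 4 as a hold, follow Arm D and restart. A site that works from the written algorithm would have to take the patient off.

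Two things are at stake. The first is patient safety and consistent care: the same child could be re-exposed to axitinib at one site and withdrawn at another. In treatment Arm A, and after crossover from Arm C, protocol therapy is both drugs, so removal also ends nivolumab on study. The second is the record: who counts as off protocol therapy for toxicity, and how long patients stayed on treatment, would depend on which line was read.

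**Working it through.** No formula applies to the contradiction itself. The check is to set the texts side by side and ask whether one reading satisfies all of them.

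**1. Where each trigger in the Figure 1 note leads in the written algorithm**

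| Trigger in the note (action: hold) | Algorithm branch | Outcome |
|---|---|---|
| More than 25 mmHg above ULN | Arm D | Hold; restart possible within 21 days |
| Up to 25 mmHg above ULN for over 14 days | Arm C, then Arm D | Hold; restart possible within 21 days |
| 35 mmHg above baseline for over 14 days | Arm C, then Arm D | Hold; restart possible within 21 days |
| Grade 4 hypertension | Arm E | Discontinue; remove from protocol therapy |

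Three of the four triggers have a restart route. Grade 4 is the exception, and the note does not mark it as one.

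**2. Whether *hold* could be shorthand for *discontinue*.** Arms C and D print *hold* in bold and Arm E prints *discontinue* in bold. Arm C twice sends a patient whose axitinib is held on to Arm D. Arm D states removal separately, as what follows a hold that has lasted too long. The algorithm therefore treats the two words as different actions. The one slip is Arm E's closing note, which uses *held* just after ordering removal.

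**3. Whether 5.2.4 settles it.** Section 5.1.2.8 lists Grade 4 hypertension among the non-hematological dose-limiting toxicities, so the wording of 5.2.4 reaches it, and 5.2.4 names no exception. Later event-specific sections are stricter than 5.2.4, however. Section 5.2.6 permanently discontinues protocol therapy for Grade 4 pleural effusion or ascites, and 5.2.8 removes patients with left ventricular systolic dysfunction of Grade 3 or higher. The natural structure is a general default with specific overrides. On that structure 5.2.4 drops out, and the conflict between the note and Arm E remains.

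**4. Whether intent can be inferred from the adult text.** Table 1 in Section 5.2.5.3, for adults hospitalized with symptomatic pressure above 180 systolic or 110 diastolic, allows either permanent discontinuation or restart one dose level lower once pressure is controlled. Both outcomes occur in this protocol, so the adult text does not show which was meant for children.

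**5. Reach.** Section 9.1 sets target accrual at 28 and a ceiling of 40. Only patients under 18 who receive axitinib are exposed, and their number is not given. The paediatric phase 1 study summarized in Section 2.3 had toxicity data on 15 patients; Cycle 1 hypertension was Grade 1 or 2, in 4 of them. If none of the 15 had Grade 4 hypertension (an assumption, since the summary does not list every later-cycle event), the one-sided 95% upper bound on the rate is 1 − 0.05^(1/15) = 1 − 0.819 = 0.181, about 18%. That is consistent with a rare event but does not exclude a few.

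**The case against.** The best defence is that the Figure 1 note is only a legend giving the immediate step. It states no restart rule and no 21-day limit for any trigger; the written branches supply those. On this view Arm E completes the note for Grade 4 just as Arm D does for the other high readings, and Arm E's own use of *held* shows the section is loose with the word. The drawn figure is also missing from the text available for this review, so its Grade 4 box could not be checked.

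Part of this stands. A reader who goes on to Arm E will find a disposition, and the figure may be clearer than its note. But the note does not call the hold a first step, and it joins Grade 4 to the very trigger that Arm D lets restart. The looseness in Arm E is a further reason to edit.

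Three stronger readings are tempting and are not supported:

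- **Three conflicting rules.** A reader might count the note, 5.2.4 and Arm E as three. The first two are both holds and are compatible, and 5.2.4 reads as a default that specific sections override. There are two incompatible outcomes.
- **A common problem.** Section 6.1 lists hypertension as a likely axitinib event (over 20%). That list does not separate grades and says nothing about the frequency of Grade 4.
- **Damage to the primary comparison.** Under Section 9.4 removal from therapy is not a progression-free survival event, and such patients are still followed. Grade 4 hypertension attributable to protocol therapy counts as a dose-limiting toxicity under 5.1.2.8 whichever action follows. A removed patient moves from cycle-based imaging to the Section 7.2 schedule, but for very few patients.

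**Conclusion.** The inconsistency is real, and it lies inside Section 5.2.5.4: the Figure 1 note says hold, Arm E says discontinue and remove, and no text gives precedence. Section 5.2.4 makes it easier to misread but is not a separate rule. The conclusion rests on the printed text alone. A drawn figure that shows Arm E's action in its Grade 4 box would reduce the practical risk but would leave the note wrong or incomplete.

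In size, it touches only Grade 4 hypertension in patients under 18 on axitinib. The rate is not given and few events are likely. The 22-event design, its alpha and its power are unaffected. It should still be corrected, because it is an instruction for a serious toxicity in children and the two readings lead to opposite dispositions. Which disposition is clinically right is not judged here.

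**What to change.** Reconcile the Figure 1 note with Arm E, including Arm E's closing note, so that one action for Grade 4 hypertension is stated throughout Section 5.2.5.4. Check the drawn figure against the agreed wording at the same time. Add to Section 5.2.4 a short pointer that the hypertension-specific rules are in Section 5.2.5. The sponsor's clinical team decides which action applies; either the note or Arm E may be the text that changes.

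The cost is a few words in the note, in Arm E and in 5.2.4, plus the figure if it needs redrawing. It can go into the next amendment. Sample size, analysis and data collection do not change.

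### Table 2 gives two outcomes for drug-related Grade 2 pneumonitis that needs steroids but resolves and tapers within 6 weeks: the row implies restart, footnote d takes the patient off drug

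*Combined protocol and SAP*

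**What the plan says.** Section 5.3, Table 2 is titled "Dose Modification Guidelines for Nivolumab-Related Adverse Events", so its pneumonitis row concerns drug-related pneumonitis.

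- **Row, Grade 2, restart column:** nivolumab is held at Grade 2 and may restart when "Toxicity resolves to Grade 0-1".
- **Row, Grade 2, discontinuation column:** there are two alternative triggers. One is toxicity unresolved within 6 weeks of the last dose. The other is "inability to reduce corticosteroid to 0.15 mg/kg (up to 10 mg) or less of prednisone or equivalent per day within 6 weeks".
- **Row, Grade 3-4:** permanent discontinuation.
- **Footnote d, marked on the word Pneumonitis in that row:** "Patients will come off study drug if steroids are required to treat drug-related pulmonary toxicity". Its only exemption is for short steroid courses given for a different condition.
- **Note under the table:** "Permanently discontinue for any severe or Grade 3 (Grade 2 for pneumonitis) drug-related AE that recurs or any life-threatening event".

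**The concern.** A stopping criterion based on failure to taper has meaning only for patients who were given steroids. Its presence in the Grade 2 row implies that steroid treatment alone does not end nivolumab, and that a patient who resolves and tapers in time can restart. Footnote d makes the need for steroids sufficient to come off drug. It has no grade limit, no time window and no taper allowance.

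Steroid-treated Grade 2 lung toxicity is foreseen elsewhere in the protocol. Section 4.2.7 permits steroids for immune-related events, and Section 5.1.2.3 names autoimmunity of the lung among Grade 2 toxicities that may need systemic immunosuppression.

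If sites follow different lines, one may re-expose a patient whom another would remove. The nivolumab risk list in Section 6.2 marks pneumonitis with its warning about severe and possibly fatal immune-mediated events. Both open arms give nivolumab, so the situation can arise in either. With a target of 28 patients (Section 9.1), different handling of even a few could affect the exposure and toxicity data that serve the secondary aim in Section 1.2.1.

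**Working it through.** No arithmetic applies, because the point concerns two text rules. The check applies each rule to the same patient and compares the outcomes. Inputs are the Grade 2 and Grade 3-4 pneumonitis cells and footnote d, all in Section 5.3, Table 2. Every case below is drug-related, as the table title requires.

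| Case | Row | Footnote d | Same outcome? |
|---|---|---|---|
| Grade 2, no steroids, resolves to Grade 0-1 within 6 weeks | May restart | Not triggered | Yes |
| Grade 2, steroids, not resolved or not tapered within 6 weeks | Discontinue | Off drug | Yes |
| Grade 2, steroids, resolved and tapered within 6 weeks | May restart, by implication | Off drug | **No** |
| Grade 3-4 | Permanently discontinue | Off drug if steroids are required | Yes: stopped under the row in any case |

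Only the third case splits. Four further steps test whether the text resolves it.

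1. **Does footnote d's exception cover it?** No. The exception is for transient steroids given for other pathology, whereas here the steroids treat the drug-related pneumonitis.
2. **Could coming off study drug mean a temporary hold?** The wording does not support that. The row already holds at Grade 2, the footnote gives no route back, and footnotes a and b use the same verb for removal from protocol therapy.
3. **Does the note on recurrence settle it?** No. By stopping for recurrent Grade 2 pneumonitis, it presupposes that some patients restart after a first episode. Restart after steroid-free resolution satisfies both rules, so the note fits either reading.
4. **What if footnote d overrides the row?** Then, in a table limited to nivolumab-related events, the row's taper clause has almost nothing left to govern. Nothing in the table states that footnotes prevail. The table can also put a footnote's stop in the cells: the rule on pancreatitis-associated diabetes in footnote b appears in its row as well. The pneumonitis cells do not repeat footnote d.

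**The case against.** The strongest reply is that footnote d qualifies the row it hangs on, as footnote c does for infusion reactions, and simply adds a third stopping trigger. Stopping triggers can coexist, and the row would still govern restart after steroid-free resolution. The taper clause recurs in many other rows, so it may be stock wording and not a deliberate plan to treat pneumonitis with steroids and resume. This reading is possible, and it is why the restart allowance must be described as implied: the restart cell says nothing about steroids. It does not remove the problem, because a site must then disregard a clause printed in the row, with no instruction to do so.

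Other provisions limit the consequences. Section 5.1.2.3 makes Grade 2 lung autoimmunity requiring systemic immunosuppression a dose-limiting toxicity, and Section 5.1 asks for the Study Chair to be told. Section 5.3.4 takes a patient off treatment where the investigator judges continued dosing a substantial risk. Both are real safeguards, but neither says which line controls. The pulmonary algorithm in Appendix V is not reproduced in the text available, so whether it helps cannot be determined.

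A reader might also infer three stronger things that the documents do not support:

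- **That the row expressly permits restart with a steroid taper.** It does so only by implication from the discontinuation column.
- **That up to 20% of patients are affected.** The Section 6.2 list places pneumonitis in a category whose ceiling is 20%. That is an all-grade heading, not an observed rate, and it says nothing about the steroid-treated Grade 2 subset that resolves and tapers.
- **That the primary comparison is biased.** Both open arms use the same table, Section 9.4 analyses PFS by intention to treat, and no differential effect is shown.

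**Conclusion.** The concern holds in a narrow form. For drug-related Grade 2 pneumonitis that is treated with steroids and then resolves and tapers within 6 weeks, the row and footnote d point to opposite outcomes. If footnote d is meant to override, the row's taper clause is effectively void.

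The size cannot be stated as a rate, because the documents give no frequency for this subset. With ceiling accrual of 40 patients (Section 9.1), the number is likely to be small. Alpha, power and sample size are unaffected. The point still merits correction: it is a stopping rule for a potentially fatal toxicity, and two sites reading the same table could act differently.

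The conclusion rests on reading the discontinuation column as a complete list of the row's own stopping criteria, and on there being no clarification in the Appendix V pulmonary figure.

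**What to change.** Reconcile the Table 2 pneumonitis row and footnote d so that a single rule applies to steroid-treated, drug-related Grade 2 pneumonitis at all sites. State it in the row's cells as well as in any footnote that remains, and check the Appendix V pulmonary algorithm against it. Which rule stands is for the sponsor's clinical team, and this review takes no position. The cost is an edit to one table cell or one footnote, with no change to the design or the analysis.
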